The study uses a randomized controlled trial design to investigate the efficacy of a virtual reality-based executive function training program for cognitive rehabilitation among 32 children between 6 and 17 years old (inclusive) with TBI. Participants will be recruited from Spaulding Rehabilitation Hospital (Boston, MA) and Kennedy Krieger Institute (Baltimore, MD), using the following inclusion and exclusion criteria:

Inclusion criteria:

- Diagnosed with moderate to severe TBI and 6-17 years at the time of injury;
- Moderate or severe TBI. Diagnosis is determined by multiple factors, including but not limited to: Glasgow Coma Scale score, additional clinical characteristics, and expert opinion by physician or therapists.
- Fluent in English-based communication
- Physicians note closest to time of enrollment does not include information on agitation, or if under observation for agitation, currently score <28 on the Agitated Behavior Scale indicating mild to no agitation.

Exclusion criteria:

- Severe physical/visual/cognitive impairments secondary to TBI such as inability to follow directions, unresponsiveness, and limited motor skills that prevent proper utilization of a VR-based training and valid administration of the study measures;
- Premorbid neurological or developmental issues such as autism, developmental delay, severe language impairment or neurologic disorder before the injury that might prevent proper utilization of a VR-based game and valid administration of the study measures, and that

- might confound the study findings;
- More than one post-injury seizure.
- Patients restricted from using electronic gaming devices

Briefly describe study procedures. Include any local site restrictions, for example, “Subjects enrolled at Partners will not participate in the pharmacokinetic portion of the study.” Describe study endpoints.

The following study procedures will be followed in this study:

Visit 1:

Baseline Assessment:

- On first day of the study, participants will complete a standard cognitive and attention assessment using virtual reality, computer, and iPad as well as several questionnaires with a researcher. These assessments will take about 60 minutes.

Intervention Session:

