- Intervention session can take place any time following the baseline assessment. Participants will be provided a tutorial to be familiar with the VR equipment, as well as a standardized interactive tutorial automatically built into the VR for completing the training tasks.
 - The VR game for the intervention group is called “Rescue the Lubdubs”. In this game, children will try to rescue an animated creature called “lubdub” by defeating the guards (training inhibitory control skills), memorizing the passcode to unlock castle gates (training working memory skills), and matching partners between the lubdub’s belly and its guards (training cognitive flexibility skills).
 - The VR game for the control group is a relaxing and immersive playground where children can throw projectiles (bees, beans, etc.) to different objects in the virtual environment (moving boards, water buckets, light bulbs, etc.). This game does not require the use of any of the executive functioning skills (i.e., inhibitory control, working memory, cognitive flexibility) and therefore serves as a placebo game for the control group.
- Participants will only be randomized to either intervention or control groups after completion of the baseline assessment. The randomization scheme is designed blocked randomization with random block sizes of 2 and 4 and 1:1 ratio for intervention and control treatment.
 - Randomization and the intervention session will be completed by an unblinded Research Assistant.
- Participants will then complete at least one (1) 30-minute intervention session. The child and their family can decide if they would like to play the game for a longer period of time. Breaks are permitted upon patient request at any time. AEs and serious AEs will be actively monitored throughout the intervention sessions. Anxiety in anticipation of the intervention will also be assessed before the intervention, while simulator sickness, perceived exertion, and subjective VR experience will be measured after the intervention.

Visit 2:

Post Intervention Assessment: Post-intervention assessment will be scheduled upon completion of the intervention session and should take place within 1 week after the intervention session. Research staff blinded to the participants’ group assignment will administer the post-training assessment, which consists of the same set of tasks as those in

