the baseline assessment, as well as VR experience questions such as motion sickness, perceived benefits and challenges, and physical exertion.

Between Visit 2 and Visit 3:

- A brief EMA-EF Survey will be sent to participants to complete daily between the post-intervention and follow-up visits, which may take about 2 minutes per day for 30 days.

Visit 3:

Follow-Up Visit

- Follow-up visits are scheduled 30 days following the post-intervention assessment (up to 12 months). Staff blinded to the participants' group assignment will administer the following measures:
 - VR and NIH Toolbox tests;
 - Conners CPT 3;
 - Children's Anxiety Meter;
 - Self-report BRIEF2, BASC-3, and PedsQL Generic Core Scales;
 - TPVT
 - Media Use Survey.
 - A parent will complete the parent-report version of BRIEF2, BASC-3, and PedsQL.

The study endpoint is the preliminary efficacy of the VICT program, defined as the changes in VR Assessment Scores, NIH Toolbox Composite Scores, and BRIEF2 Global Scores between baseline and post-intervention and between baseline and follow-up assessment.

For studies involving treatment or diagnosis, provide information about standard of care at Partners (e.g., BWH, MGH) and indicate how the study procedures differ from standard care. Provide information on available alternative treatments, procedures, or methods of diagnosis.

The virtual reality intervention is designed to be supplementary to standard of care at Spaulding Rehabilitation Hospital. Therefore, all participants will still receive standard of care as determined by their doctors regardless of participation of this study or random assignment to the intervention or control group.

Describe how risks to subjects are minimized, for example, by using procedures which are consistent with sound research design and which do not unnecessarily expose subjects to risk or by using procedures already being performed on the subject for diagnostic or treatment purposes.

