## **Data Analysis Plan (Updated for 2nd NCE Period)**

First, descriptive analysis will be conducted to compute the means and standard deviations of all predictor and outcome variables listed in the Measures section. Means of baseline covariates, including age, sex, injury severity, recency of injury, verbal intelligence, anxiety, and prior VR gaming experience, will be compared using independent samples t-test between intervention and control groups. Due to the randomization, we expect that most of covariates will show non-significant differences between assignment groups. These variables will be considered balanced between groups and not included as covariates in the analyses that follow. For the covariates that are found imbalanced between groups (perhaps due to the small sample size, they will be controlled statistically in the analyses that follow. This approach will reduce the number of covariates in respective statistical models and maximize the statistical power of each proposed analysis.

Next, hypotheses for each specific aim will be evaluated.

- **Aim 1**
  - *H1.1 and H1.2* will be tested using a *multi-level model* where scores on VR tasks and NIHTB- CB tasks (H1.1) or BRIEF2 scores (H1.2) will serve as respective dependent variables. Study visit (pre, post, follow-up) will serve as a predictor that is nested within subjects and condition will serve as a between-subject predictor.
  - *H1.3* will be tested using a *multi-level model* where time (Day 1 – Day 30) is nested within subjects. The EMA-EF scores will be the DV, allowing each patient to have unique initial level and rate of change in daily EF across the 30-day period.
  - Multi-level models have been used in studies with sample sizes as small as single cases. Therefore, our study with a sample size of 15 will be sufficient to conduct multi-level modeling analyses. Furthermore, in all multi-level models for Aim 1, we will use the Kenward-Roger correction in degrees of freedom^2 to further minimize small sample size bias and prevent inflation of type I error rates in estimation.
- **Aim 2**
  - *H2.1* will be tested using the same approach as H1.1-H1.2 via *multi-level modeling*. Study visit (pre, post, follow-up) will serve as a predictor that is nested within subjects and condition will serve as a between-subject predictor. The only difference is that for this model CPT 3 scores will serve as DV.

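### The only VR equipment tutorial described comes after the baseline VR test, so VR change scores may include learning the device; move it before baseline and read VR change only between arms

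*Protocol*

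**What the plan says.** In the protocol's Research Design and Methods, Visit 1 opens with the Baseline Assessment, at which "participants will complete a standard cognitive and attention assessment using virtual reality, computer, and iPad". The Intervention Session is listed next, with the timing "Intervention session can take place any time following the baseline assessment". Two kinds of instruction appear under that session and nowhere else in the visit descriptions. One is orientation to the device ("Participants will be provided a tutorial to be familiar with the VR equipment"). The other is "a standardized interactive tutorial automatically built into the VR for completing the training tasks". The device orientation is for participants in general, not for one arm.

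Both arms then play in VR for at least one 30-minute session; "The VR game for the control group is a relaxing and immersive playground". Allocation comes after baseline: "Participants will only be randomized to either intervention or control groups after completion of the baseline assessment". Visit 2 repeats the baseline tasks, and Visit 3 includes the VR tests again.

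The endpoint paragraph gives preliminary efficacy as "defined as the changes in VR Assessment Scores, NIH Toolbox Composite Scores, and BRIEF2 Global Scores", from baseline to post-intervention and from baseline to follow-up. It does not mention the control group. Hypothesis 1.1 in the Specific Aims does, since it predicts greater improvement than in controls. For that hypothesis the SAP's Data Analysis Plan names study visit and condition as predictors and does not name their interaction. The SAP's baseline covariates include "verbal intelligence, anxiety, and prior VR gaming experience"; a covariate enters the models only if the arms are found to differ on it.

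**The concern.** Baseline and later VR scores may be taken under different conditions. At baseline a novice may still be working out the viewer and the controls. By Visit 2 every child has had the tutorial and a session of play. A change score would then combine change in executive function with learning to use the device.

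The documents give reason to expect that familiarity matters and differs between children. Ages run from 6 to 17, the SAP treats previous VR gaming as a covariate, and the protocol's risk section links motion-sickness symptoms mainly to previous gaming and VR experience.

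Two things are at stake. First, improvement within an arm could be read as efficacy when part of it is familiarisation. Second, avoidable variation enters a comparison that is already small: 32 children in the protocol and 15 in the SAP.

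**Working it through.** The documents give no SD, correlation or learning effect for the VR scores, so there is no figure of the plan's to reproduce. The order of procedures is a matter of reading, set out above. The consequences below use assumed values, in units of the baseline SD (SD = 1).

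**Inputs**
- Baseline-to-post correlation r = 0.5 or 0.7 (assumed).
- Mean familiarisation gain L = 0.2, 0.5 or 0.8 (assumed).
- Between-child SD of the gain, g = 0.2, 0.3 or 0.5, independent of the scores (assumed).
- True training effect zero; two-sided test at 0.05.
- N = 15 (SAP; 7 and 8 per arm) or 32 (protocol; 16 per arm under 1:1 allocation).

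**1. Gain common to both arms, between-arm contrast.** Each arm's mean change is raised by L, so the difference in change is shifted by L − L = 0. Type I error stays at 0.05 for every L.

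**2. Gain common to both arms, change read without the control comparison.** A one-sample t test of change in all children pooled has noncentrality L√N / √(2(1 − r)). For L = 0.5 and N = 15 this is 0.5 × 3.873 / 1 = 1.94 at r = 0.5, and 0.5 × 3.873 / 0.775 = 2.50 at r = 0.7. The probability of a significant improvement with no training effect is:

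| L | N = 15 | N = 32 |
|---|---|---|
| 0.2 | 0.11–0.15 | 0.20–0.29 |
| 0.5 | 0.44–0.64 | 0.78–0.94 |
| 0.8 | 0.82–0.96 | 0.99–1.00 |

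Each range runs from r = 0.5 to r = 0.7.

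**3. Gain that varies between children.** With r = 0.7 the variance of change is 2(1 − 0.7) = 0.6. Adding the gain makes it 0.6 + g². The standard error of the arm difference is √(0.6 + g²) × √(1/n₁ + 1/n₂).

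| g | Variance ratio (0.6 + g²)/0.6 | SE ratio | SE, N = 15 | SE, N = 32 |
|---|---|---|---|---|
| 0 | 1.00 | 1.00 | 0.40 | 0.27 |
| 0.2 | 0.64/0.6 = 1.07 | 1.03 | 0.41 | 0.28 |
| 0.3 | 0.69/0.6 = 1.15 | 1.07 | 0.43 | 0.29 |
| 0.5 | 0.85/0.6 = 1.42 | 1.19 | 0.48 | 0.33 |

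These rows compare the whole of the familiarisation noise with none. They are therefore an upper limit, for each g, on what moving a tutorial could save.

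**4. Gain that differs between arms.** Any difference in mean gain passes one-for-one into the contrast. If the arms differed by half of L, for L from 0.2 to 0.8, the rejection rate with no training effect would be 0.05–0.15 at N = 15 and 0.06–0.29 at N = 32. No passage shows that device learning differs by arm.

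**The case against.** The strongest reply is that the design already deals with the main mechanism. Both arms receive the equipment tutorial, controls play an active VR game, and Hypothesis 1.1 is a comparison with controls. This stands: a shared gain cancels, and a reader who infers from the order of procedures that the treatment effect is biased goes further than the documents allow. Bias needs learning that differs by arm. That would come from the two games, which stay after baseline wherever the equipment tutorial is placed. Hypothesis 1.1 itself describes the VR tasks as trained, so practice on them is part of the intended difference.

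A reader might also infer that children have no orientation at all before the baseline VR test. The documents do not support that either. The protocol is a summary form asking for brief descriptions, a researcher is present at the assessment, and part of the SAP was not available for this review, although its analysis plan refers to a Measures section. The VR test may carry its own instructions or practice trials.

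The plan also collects prior VR experience and adjusts for it if the arms differ. This helps only in part: adjustment is conditional on a finding of imbalance, and balanced arms would still carry the between-child noise.

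Finally, the SAP heading refers to a second NCE period and the sample there is 15. That suggests, without proving, that enrolment is well advanced, in which case reordering would help few children and leave two baseline conditions in a small sample. This is a fair cost and is the reason for a flag.

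**Conclusion.** The point holds in a limited form and is of minor to moderate weight. As the protocol is written, the only equipment tutorial described follows the baseline VR test, and change from that baseline is a named endpoint. The randomised contrast is not biased by a gain that both arms share. Two costs remain.

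- **Interpretation.** The endpoint wording leaves out the control comparison and the SAP names no visit-by-condition term, so the plan does not rule out reading within-arm or pooled change as efficacy. Under an assumed shared gain of 0.5 SD, that reading would show a significant improvement with no training effect 44% to 64% of the time at N = 15 and 78% to 94% at N = 32.
- **Precision.** The standard error of the arm difference rises by at most 3% to 19% for an assumed gain SD of 0.2 to 0.5 and a correlation of 0.7. A short tutorial is not equivalent to a tutorial plus 30 minutes of play, so it would recover only part of this.

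All of these sizes rest on assumed inputs. The order of the steps and the endpoint wording do not.

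**What to change.** 1. Move the existing equipment tutorial to the start of Visit 1, before scored baseline VR trials, for every child. If equivalent orientation already precedes those trials, say so in the protocol; no move is then needed. Keep the task-specific tutorial in the intervention session.
2. State in the endpoint paragraph and the SAP that VR change is interpreted only as the between-arm difference in change (the visit-by-condition term), not as improvement within an arm.
3. If enrolment is under way, flag children tested under the existing order and describe their VR change as possibly including familiarisation.

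A sensitivity analysis of change from Visit 2 to Visit 3 may look attractive because both scores follow familiarisation. It should not be used for this purpose: it omits the interval in which training takes place and so addresses retention, not efficacy. Comparing follow-up level alone is no cleaner in practice. Its variance is about 1 on the scale used here, against 0.64 to 0.85 for change that includes familiarisation noise, if the same assumptions are applied to follow-up.

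The cost is one or two protocol sentences, a few more minutes before baseline testing, and the flag. The change does not remove arm-specific learning from the two games.

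### Blinded assessors at Visit 2 are assigned VR experience questions whose answers could reveal which game the child played, and no safeguard is stated

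*Protocol*

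**What the plan says.** All of the following is in the Protocol, Research Design and Methods.

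- **Intervention session (Visit 1).** "Randomization and the intervention session will be completed by an unblinded Research Assistant". After the session, "simulator sickness, perceived exertion, and subjective VR experience will be measured after the intervention". The person who collects these measures is not named.
- **The two games.** The intervention game has the child rescue creatures by beating guards, "memorizing the passcode to unlock castle gates (training working memory skills"), and matching partners. The control game is a playground for throwing objects at targets, and it is designed to call on none of the three executive function skills.
- **Visit 2, within a week of the session.** The Protocol states: "Research staff blinded to the participants’ group assignment will administer the post-training assessment, which consists of the same set of tasks as those in" (meaning those given at baseline). Its closing words add one more element: "as well as VR experience questions such as motion sickness, perceived benefits and challenges, and physical exertion".
- **Visit 3.** "Staff blinded to the participants' group assignment will administer the following measures", followed by the list of tests and questionnaires.

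The study endpoint is the change in VR, NIH Toolbox and BRIEF2 scores from baseline to post-intervention and from baseline to follow-up, so it draws on both visits.

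**The concern.** The trial has built a separation between the person who knows the allocation and the people who test the child. That separation guards against differences between arms in how tests are introduced, how much the child is encouraged, and how breaks and prompts are handled.

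The Visit 2 sentence weakens it. It gives the blinded assessor a question about what the child found beneficial or difficult in VR. If the child answers in terms of the game, the assessor may learn the arm. At stake is the credibility of the blind for whatever testing that assessor does afterwards, at Visit 2 or at Visit 3.

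**Working it through.** No arithmetic applies. The documents give no unblinding rate and no size for assessor bias, so the check is a reading of the passages against each other.

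**1. Who asks the questions?** The outcome tasks and the VR experience questions are objects of one sentence with one administrator, the blinded staff. No other collector is named for Visit 2.

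**2. Could an answer identify the arm?** The games share almost no content. A mention of passcodes or guards points to one arm, and a mention of throwing things points to the other. Because the control game is designed to make no executive function demand, even a general remark about difficulty may be informative.

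**3. Are all the items equally revealing?** No. The baseline battery uses VR (Visit 1, Baseline Assessment) and is repeated at Visit 2, so motion sickness and exertion ratings may concern that VR assessment, which both arms receive. Perceived benefits is harder to read that way, since the assessment is not meant to confer a benefit. The risk sits mainly with the benefits and challenges items.

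**4. Which testing could be exposed?** This depends on facts the Protocol does not state:

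| Where the questions fall in Visit 2 | Staff at Visit 3 | Visit 2 testing | Visit 3 testing |
|---|---|---|---|
| After outcome testing | Different, answers not visible | Not exposed | Not exposed |
| After outcome testing | Same, or answers visible | Not exposed | May be exposed |
| Before outcome testing | Different, answers not visible | May be exposed | Not exposed |
| Before outcome testing | Same, or answers visible | May be exposed | May be exposed |
| Completed out of the assessor's sight and not seen later | Any | Not exposed | Not exposed |

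The table covers this route to unblinding only. The Protocol allows every row. It gives no order, no mode of completion, no rule on staff at Visit 3, and no instruction against discussing the game. The SAP's Data Analysis Plan does not take up assessor blinding.

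**5. Which outcomes could be affected?** The baseline assessment is done with a researcher, using VR, computer and iPad tasks and questionnaires. Device scoring leaves little room for bias in scoring, but the researcher still introduces the tasks and supports the child through them. BRIEF2, BASC-3 and PedsQL are self- or parent-rated, and the daily EMA-EF survey is sent to participants. An assessor has less influence on these.

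**The case against.** **The items may be structured self-report.** The Data and Safety Monitoring section describes the VR experience data as self-reported through designated instruments attached to the Protocol. Those instruments are not in the available text. If they are rating scales, a child may never describe the game. This stands in part: nobody can say from the documents that children will often name it. But self-report does not mean out of the assessor's sight. The topics named in that section are exertion, motion sickness, and fun, pleasure and motivation; benefits and challenges are not among them.

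**The items may concern the VR assessment, not the game.** This is plausible for motion sickness and exertion, and those items are left alone below. It fits perceived benefits poorly.

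**The unblinded assistant may already collect this.** A reader might infer so, because the assistant runs the session and VR experience is measured after it. The Protocol does not say who collects it, so it cannot be claimed that the blinded staff's questions are redundant.

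**Most outcomes are computerised or self- or parent-reported.** This stands, and it limits the likely size of any bias. It does not remove the assessor's part in instructing and encouraging the child.

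**Conclusion.** The point holds as a weakness in procedure. The plan puts potentially unblinding questions in the blinded assessor's hands and states nothing to contain the effect. It rests on two readings: that the single Visit 2 sentence means what it says about who administers the items, and that perceived benefits and challenges refer at least partly to the game.

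Two stronger readings are tempting, and the documents support neither.

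- **That assessors are unblinded before they test at both visits.** No order is given within Visit 2, and the VR questions are named after the tasks. If they come last, Visit 2 testing is untouched by this route. Visit 3 is exposed only if the same staff return or can see the answers, and the Protocol neither says nor excludes this.
- **That a false-positive rate can be attached.** That would need an assumed shift in scores, for which the documents give no basis. A simple two-sample calculation would also not match the plan. The SAP uses t-tests only for BASC-3 and PedsQL at follow-up, which are ratings by child or parent. The VR, NIH Toolbox and CPT 3 scores go into multi-level models.

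The size is therefore unknown and probably limited. The change is worth making because it is cheap and protects a blind the trial already relies on.

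**What to change.** Take the benefits and challenges items out of the blinded assessor's hands, in one of two ways:

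1. The unblinded research assistant who runs the session collects them with the post-session measures.
2. The child or parent completes them at the end of Visit 2, after all outcome testing, on a form that the blinded assessor does not see then or later.

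Keep the motion sickness and exertion ratings that concern the Visit 2 VR assessment itself, so that tolerability data for safety review are not lost. Add a sentence that blinded staff do not discuss the game with the child or family at Visits 2 or 3.

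The cost is a change in who sees these answers and when, with no new staff, measures or visits. The first option has a small downside: benefits reported straight after the session may differ from those reported up to a week later. The second keeps the Visit 2 timing and avoids this.
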